1.0. BACKGROUND

1.1 Study Rationale

Definitive assessment of the efficacy of preoperative Pulmonary Rehabilitation (PR) can only be addressed through a randomized, controlled clinical trial. Performing this protocol with a multicenter design ensures that the results are not unique to a narrow population or center.

We plan to obtain definitive evidence for the effectiveness of a short preoperative PR protocol on the recovery from a curative surgical resection in patients with non-small cell lung cancer (NSCLC) and Chronic Obstructive Pulmonary Disease (COPD).

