5.2.2 Training of the Site Personnel for Pulmonary Rehabilitation

Patients **may not** be registered to this study until at least one person from each site has been approved to perform pulmonary rehabilitation. It is recommended that each site have a trained backup person to cover absences.

This study requires that the person who will deliver the intervention is approved by [name] staff. Each person who administers the intervention must be certified.

Each participating site will have one or two people who are trained to deliver the intervention (nurse, respiratory therapist or physiotherapist, or trained study coordinator).

Training should start at least a month prior to enrollment. It is anticipated that the one on one training will require four 30 minute calls with homework in between.

[name] staff will train the PR staff or selected interventionist for the delivery of the intervention. Training documents and videos will be sent to the participating site by [name] staff. Institutional staff who will be delivering the intervention will have demonstrated an understanding of the content of these materials. These interventionists will be trained in steps, which will include reviewing materials and demonstrating proficiency in leading the patient through the techniques. After the individual is comfortable with the intervention protocol s/he is to demonstrate the exercises while being recorded (cellphone, video camera). The recording can be sent to [REDACTED]. Once the recording has been reviewed, the individual will have a one-on-one online training via Skype or FaceTime with [name] staff. Once it has been determined that the individual is able to deliver the intervention, [name] staff will email notice of this approval (in the form of a "confirmation of certification form") to the site, which will need to submit this approval to the CTSU per sections 4.3.2 and 4.3.3.

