11.2 Sample Size, Accrual Time, and Study Duration

11.2.1 Sample Size

A total of 194 patients (97 in each group) will be accrued to this study. This sample size includes a 10% adjustment to account for attrition and will provide at least 80% power for testing each aim of the study. Based on estimates from the pilot study, this sample size will provide 80% power to detect a 25% difference in complication rates, a 3-day difference in chest tube days, 3 day difference in length of stay, and a half standard deviation difference in QOL endpoints.

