11.3.2 Analysis Plan

Differences in length of stay between arms will be tested using a two-sample, two-sided t-test. Wilcoxon nonparametric testing will be used for analyzing continuous outcomes that are skewed and not approximately normally distributed. Fisher's exact tests will be used to test for differences in categorical variables between arms. All tests will be two-sided with a 0.05 significance level. Linear models will be created to test the effects of treatment after adjusting for the baseline characteristics of age, gender, and lung function.

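### The adjusted length-of-stay and QOL models omit site; a random site intercept would be a cheap, modest gain in precision

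*Combined protocol and SAP*

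**What the plan says.** Section 1.1 gives the reason for using several centres: "Performing this protocol with a multicenter design ensures that the results are not unique to a narrow population or center". Sections 1.3 and 11.1 do not say how many centres there will be.

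Section 4.6 stratifies randomisation by very severe lung function, neo-adjuvant chemotherapy, and open versus VATS surgery. Site is not among the factors.

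Section 11.3.2 tests length of stay with a two-sample t-test, and uses Wilcoxon for skewed continuous outcomes. It then adds the adjusted analysis: "Linear models will be created to test the effects of treatment after adjusting for the baseline characteristics of age, gender, and lung function". Section 11.4.1 analyses QOL in the same way as the primary endpoint. Section 11.4.2 adds repeated-measures and regression models with the same covariates.

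On delivery of the intervention, section 5.2.2 states: "Each participating site will have one or two people who are trained to deliver the intervention". Each interventionist must be centrally certified, and section 7.1 has the same video played in all 10 clinic sessions.

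**The concern.** Length of stay can differ between hospitals for reasons unrelated to the trial arm. The protocol sets no common discharge criteria, and controls receive each site's usual care (section 7.2). Randomisation is not stratified by site, so the arms can be uneven within a site by chance. With no site term, any between-site variation goes into the residual and such unevenness is not adjusted for. At stake is the precision of the adjusted estimates.

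A second, separate question concerns the interventionists. They work only with the rehabilitation arm. If they differ in effectiveness, the treatment effect itself varies by site, and no planned analysis looks at this.

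**Working it through.** **Inputs from the plan (sections 11.2.1 and 11.3.2).** "A total of 194 patients (97 in each group) will be accrued to this study", with a 10% attrition allowance. The effect is a "3 day difference in length of stay". The sample size "will provide at least 80% power for testing each aim of the study". On the error rate, "All tests will be two-sided with a 0.05 significance level".

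**Inputs assumed.** The SD of length of stay, the ICC (share of length-of-stay variance lying between sites) and the number of sites are not given. Section 11.2.1 says only "Based on estimates from the pilot study".

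**1. The plan's own figure.** Evaluable per arm: 97 × 0.90 = 87.3, taken as 87. In reverse, 87 / 0.90 = 96.7, which rounds up to 97, or 194 in total. The attrition arithmetic reproduces. The 80% power for 3 days cannot be checked without an SD. The SD it implies is

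SD = 3 / [(1.960 + 0.842) × √(2/87)] = 3 / 0.4248 ≈ 7.06 days.

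**2. Upper bound on the gain.** If a site term removed all between-site variance at no cost, the standard error would shrink by √(1 − ICC):

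| ICC | SE ratio | Detectable difference at 80% power (days) | Power for 3 days |
|---|---|---|---|
| 0 | 1.000 | 3.00 | 80.0% |
| 0.05 | 0.975 | 2.92 | 82.0% |
| 0.10 | 0.949 | 2.85 | 84.0% |
| 0.20 | 0.894 | 2.68 | 87.9% |

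This ignores chance imbalance of arms within sites and the cost of estimating site effects.

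**3. Realised gain, by simulation.** Settings: 174 patients, SD 7.06, a 3-day effect, uneven site sizes, randomisation not stratified by site, random intercept fitted by REML, 3,000 trials per setting. Power in %, t-test then random intercept:

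| ICC | 5 sites | 10 sites | 20 sites | 30 sites |
|---|---|---|---|---|
| 0 | 80.5, 80.6 | 79.0, 79.1 | 79.2, 79.4 | 79.6, 79.8 |
| 0.05 | 80.3, 81.3 | 79.8, 81.0 | 79.0, 80.0 | 79.4, 80.3 |
| 0.10 | 80.8, 83.2 | 80.0, 82.1 | 79.5, 81.6 | 79.9, 81.3 |
| 0.20 | 83.4, 88.1 | 81.1, 87.5 | 79.2, 84.6 | 79.1, 84.1 |

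The Monte Carlo error of one power figure is √(0.8 × 0.2 / 3000) ≈ 0.7 points. A second run of this design with 10 and 20 sites gave gains of 0.7 and 0.7 points at ICC 0.05, 1.9 and 2.3 at 0.10, and 6.1 and 6.3 at 0.20. No setting lost power materially, including those with no site variance.

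**4. Fixed site effects are less safe.** In 4,000 trials per setting with 20 sites and ICC 0.05, power was 79.8% for the t-test and 76.5% with fixed site effects. This is why the intercept should be random.

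**5. Validity.** With site effects common to both arms, type I error was 4.7-5.8% for the t-test and 4.4-5.9% for the random intercept.

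**6. Effects confined to the rehabilitation arm.** Assume site-specific effects in that arm worth 2-10% of total variance, averaging zero over a population of sites, with 5, 10 or 20 sites and ICC 0.05. Type I error was then 5-18% unadjusted and 6-19% with a fixed site main effect. A site main effect does not address this.

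**The case against.** The strongest case against is that nothing here is an error. Randomisation covers chance imbalance within sites, and an analysis without site is valid when randomisation was not stratified by site. Nothing in the documents describes discharge practice by site or sizes between-site variation. The model concerned supports the t-test or Wilcoxon test rather than replacing it. All of this stands, and it limits the point to an optional improvement.

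A reader might infer more in four ways:

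- **That ignoring site biases or invalidates the primary test.** Step 5 shows otherwise for site effects common to both arms.
- **That power of the primary test would rise to 82-88%.** Those are the upper bounds of step 2. The realised gain is smaller and belongs only to the adjusted model.
- **That interventionist differences are noise a site intercept removes.** They act in one arm only, so they are treatment-effect heterogeneity (step 6). Central certification and the session video should limit them.
- **That section 1.1 promises a test of consistency across centres.** It gives a reason for the design, not a hypothesis, and a random intercept alone would not test it.

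**Conclusion.** The omission is confirmed: site is in neither the stratification nor any planned model. The consequence is some loss of precision in the adjusted length-of-stay and QOL analyses, without bias and without any error in the stated sample size. For length of stay, the recoverable power is about 0-1 point at ICC 0.05 or below, 1-3 points at 0.10 and 4-6 points at 0.20, starting from about 80%. These figures rest on an assumed SD of about 7 days, 87 evaluable patients per arm, 5 to 30 sites and an ICC that the documents do not supply. No corresponding figure was computed for QOL. This is worth doing because it is cheap, not because the plan fails without it.

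**What to change.** In section 11.3.2, add a random intercept for enrolling site to the adjusted linear model for length of stay, beside arm, age, gender and lung function. Do the same in the QOL models of section 11.4.2, and report the estimated between-site variance. As a separate sensitivity analysis, add a site-by-arm random effect, labelled as a check on treatment-effect heterogeneity. The t-test and Wilcoxon test stay as planned.

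The cost is slightly more analysis work. Site is known from registration, so no new data or patients are needed. If sites are few or very small, the site variance may be estimated as zero, and the model then reverts to the planned one.

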11.4 Supplementary Analysis Plans

11.4.1 Secondary Endpoints

End points that will address AIM 2 (baseline and at 3 and 6 months after hospital discharge):

Post-Operative Pulmonary Complications: The following events will be considered post-operative pulmonary complications: pneumonia (new infiltrate + either fever (>38.5 C) and white cell count $>11,000$ or fever and purulent secretions), severe atelectasis (requiring bronchoscopy), prolonged chest tubes (>6 days), and respiratory failure (intubation or prolonged mechanical ventilation (>24 hours)). These outcomes will be obtained by chart review by a nurse trained in the abstraction of the desired outcomes from the medical records and blinded to treatment assignment.

Chronic Respiratory Questionnaire (CRQ) (four domains: dyspnea, fatigue, emotional function and mastery). This instrument will be the primary tool to assess QoL given that it was specifically designed for COPD. Specifically, the CRQ represents one of the most well-known, widely-applied, and psychometrically-sound patient reported outcomes for use in clinical trials involving patients with COPD. The CRQ has been validated and has demonstrated a reliable quality of life measures for patients with chronic airflow limitations. A 0.5 point will be considered significant and was considered in the sample size calculation as that difference as is the well-established MCID (minimally clinically important difference) for the instrument. Analysis for the QOL outcomes will be identical to that for the primary endpoint. We include the scores from the dyspnea questionnaire under the generic umbrella term as a domain of QOL.

LASA (single-item numerical analogue quality of life Questionnaire) individual QOL domain scores. All of these questionnaires have been validated previously for lung cancer patient populations and for assessment of patient-reported outcomes in similar trials. LASA items have been validated as general measures of global QOL dimensional constructs in numerous settings and have been constructed and validated at Mayo Clinic for use in cancer patients. These single-item assessments have become the most used assessments in all NCI-sponsored cancer control studies.²⁸

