2.2 Secondary objectives

2.2.1 To prospectively determine the effect of 10 sessions of customized preoperative PR on the number of postoperative complications in patients that undergo a lung cancer resection and have COPD compared to a matched control group.

Hypothesis: Ten sessions of customized preoperative PR will significantly reduce the number of postoperative pulmonary complications.

2.2.2 To prospectively determine the effect of a 10-session preoperative PR on the trajectory of quality of life at 3 and 6 months after the curative resection compared to a matched control group.

Hypothesis: Ten sessions of customized preoperative PR will significantly and meaningfully (more than the minimal clinically important difference) improve quality of life after surgery compared to a control group.

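### Does giving the quality-of-life effect as half a standard deviation in section 11.2.1 and as 0.5 CRQ point in section 11.4.1 undermine the power claim?

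*Combined protocol and SAP*

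**What the plan says.** Section 11.2.1 fixes the size of the trial: "A total of 194 patients (97 in each group) will be accrued to this study". It adds that "This sample size includes a 10% adjustment to account for attrition", and that the number "will provide at least 80% power for testing each aim of the study". The next sentence cites pilot-study estimates and lists four differences said to have 80% power: one in complication rates, one in chest tube days, one in length of stay, and "a half standard deviation difference in QOL endpoints".

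Section 11.4.1 makes the CRQ the main quality-of-life instrument and says "A 0.5 point will be considered significant and was considered in the sample size calculation". The same sentence identifies 0.5 point as the instrument's MCID. It sends the quality-of-life outcomes to the primary-endpoint analysis, which section 11.3.2 describes as a two-sample t-test, or Wilcoxon if the data are skewed, with supporting linear models. Section 11.3.2 also states: "All tests will be two-sided with a 0.05 significance level".

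The hypothesis under section 2.2.2 is that rehabilitation "will significantly and meaningfully (more than the minimal clinically important difference) improve quality of life after surgery compared to a control group". Section 9.1 gives the CRQ item scale as 1 to 7. No CRQ standard deviation appears, either overall or by domain.

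**The concern.** Half a standard deviation and half a point are different quantities unless the SD is exactly 1.0 point. Section 11.4.1 says the half-point difference entered the sample size, but section 11.2.1 shows no input in points. Nor does its 80% reproduce for half an SD, because the design has clearly more than that. It is natural to suspect that one figure was mistaken for the other and that power for the MCID was never worked out.

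The stake would be how a null result is read. The CRQ is the lead quality-of-life measure and the hypothesis refers to the MCID. A reader who takes the power statement at face value could treat a non-significant CRQ result as good evidence against a meaningful benefit. If the true SD were, say, 1.4 points, power for 0.5 point would be about 65%, and that reading would be too strong.

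Two smaller points add to the unease. The word used for the 0.5-point threshold in section 11.4.1 can be confused with statistical significance. And if the true difference equals the MCID, the observed difference exceeds it only about half the time.

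**Working it through.** **Inputs.** 97 per arm and 10% attrition (section 11.2.1); two-sided 0.05 and a two-sample t-test (sections 11.3.2 and 11.4.1); effects of 0.5 SD (section 11.2.1) and 0.5 point (section 11.4.1). The CRQ SD is not given, so a range is assumed.

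**Evaluable patients.** 97 × 0.9 = 87.3, so 87 per arm.

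**The plan's figure: power at half an SD.** By normal approximation, power = Φ(d·√(n/2) − 1.96) = Φ(0.5 × √43.5 − 1.96) = Φ(3.298 − 1.96) = Φ(1.338) = 0.91. The noncentral t gives 90.6%. With all 97 per arm it is 93%. If Wilcoxon is used, with an assumed relative efficiency of 0.864 to 0.955, it is 86% to 89%. The bare 80% is not reproduced; the floor of at least 80% is met in every variant.

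**Patients needed for exactly 80% at half an SD.** n = 2 × (1.96 + 0.842)² / 0.5² = 62.8, so 63 per arm. After attrition, 63 / 0.9 = 70 per arm, or 140 in total. The planned 194 is well above this.

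**Smallest effect with 80% power at 87 per arm.** (1.96 + 0.842) × √(2/87) = 2.802 × 0.1516 = 0.425 SD; the t-test gives 0.427 SD.

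**Largest SD at which 0.5 point keeps 80% power.** 0.5 / 0.427 = 1.17 points. Under Wilcoxon with the efficiencies above, multiply by √0.864 to √0.955, which gives about 1.09 to 1.14 points.

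**Power for 0.5 point by assumed SD (t-test, 87 per arm).**

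| SD (points) | 0.8 | 1.0 | 1.1 | 1.17 | 1.2 | 1.3 | 1.4 | 1.5 |
|---|---|---|---|---|---|---|---|---|
| Power | 98% | 91% | 85% | 80% | 78% | 71% | 65% | 59% |

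**Why quality of life may have power to spare.** One sample size serves four listed outcomes, so they cannot all be expected to sit at exactly 80%. A 25-point drop in complications, tried from control rates of 30% to 70%, has at least 91.6% power at 87 per arm by normal approximation. Length of stay could be the limiting outcome: a 3-day difference has 80% power at an SD of 3 / 0.425 = 7.06 days. That SD is an illustration, not a figure in the plan.

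**How a null CRQ result would read.** The 95% interval for the difference has half-width 1.96 × SD × √(2/87) = 0.297 × SD. That is 0.30 point at an SD of 1.0, 0.35 at 1.17 and 0.45 at 1.5. The trial's own SD sets this width; the planning SD plays no part.

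**The case for a change.** The strongest reply is that a power claim resting on an unprinted number cannot be checked, and that power is sensitive to that number: moving the SD from 1.1 to 1.3 points takes it from 85% to 71%. Section 11.4.1 says the half-point difference was used in the sizing, and section 11.2.1 does not show it. Since section 11.2.1 relies on pilot estimates, the SD should have been available to report. Adjustment for baseline CRQ might protect power at larger SDs, but section 11.3.2 names only age, gender and lung function as covariates, so I do not rely on that.

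The factual part stands. The units differ, the SD is missing, and the document alone cannot confirm the power for 0.5 point. The inference that the claim is therefore unsupported does not follow. Section 11.2.1 summarises all quality-of-life endpoints together, and these include the LASA and MRC scales as well as the CRQ, so a standardised effect is a reasonable common currency. Section 11.4.1 speaks of the CRQ alone. A pilot SD near 1 point makes both statements true, and any SD up to about 1.17 keeps the 80% under the t-test.

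The two smaller points carry little weight. Section 11.4.1 explains in the same sentence that its threshold is the MCID, so the word choice is a matter of copy-editing. Section 2.2.2 states a hypothesis and sets no decision rule: the planned tests are ordinary two-sided tests at 0.05, and none is against the MCID.

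**Conclusion.** No change to the plan follows. The two sections use different units for the quality-of-life effect and the linking SD is not printed, but no stated figure is shown to fail. The floor of at least 80% holds for half an SD with room to spare (about 91% at 87 per arm), and the bare 80% in the following sentence is loose in the conservative direction. For the 0.5-point MCID, power is about 91% if the SD is 1.0 point, stays at or above 80% up to about 1.17 points, and falls below only beyond that. Nothing in the documents says on which side of 1.17 the pilot SD lay.

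This rests on 10% attrition, equal arms and the two-sample t-test; under Wilcoxon the limit on the SD is somewhat lower. The endpoint is secondary. Reporting the pilot SD would leave the sample size, the tests and the estimates as they are. A null CRQ result can be judged from the observed difference and its interval, which depend on the trial's own SD. This is an unreported detail and a looseness of wording that an analyst can handle without amending the plan.

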6.2 Patient questionnaire booklets

All patient questionnaire booklets for A221502 are to be ordered prior to the registration of any patients. Baseline booklets will be administered in clinic at the time that the patient is randomized. Samples of all questionnaire/booklets are available in Appendices I and II, for reference and IRB submission only. **They are not to be used for patient completion.**

Post-surgery booklets (month 3 and month 6) should be mailed by institutional staff to patients 1 week before the 3 and 6 month time points. Patients will be instructed to mail the booklets back to their registering site for entry into the iMedidata RAVE.

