11.4.2 Secondary Analysis

Longitudinal analysis for the relationship between QOL and the intervention will be handled by repeated measures analysis of variance modeling and multiple regressions. Finally, a logistic regression model will be used to identify which variables are most closely associated with the dependent variable of patients who experience either clinically significant deficits in QOL (one regression model). The modeling processes will include the aforementioned covariates to control for spurious correlations.

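### The QOL analysis names no baseline QOL score as a covariate, although baseline CRQ, LASA and MRC are collected, and does not say how baseline enters the repeated-measures model; the cost is precision on a secondary endpoint

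*Combined protocol and SAP*

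**What the plan says.** All places are in the combined protocol and SAP.

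- **Data.** The study calendar (5.5) marks MRC, CRQ and LASA at baseline and at 3 and 6 months. On timing, 6.2 says: "Baseline booklets will be administered in clinic at the time that the patient is randomized".
- **Aim.** Objective 2.2.2 concerns the "trajectory of quality of life at 3 and 6 months after the curative resection".
- **Main QOL analysis (11.4.1).** "Analysis for the QOL outcomes will be identical to that for the primary endpoint". Under 11.3.2 that means a two-sample t-test, or Wilcoxon for skewed outcomes, plus linear models "adjusting for the baseline characteristics of age, gender, and lung function".
- **Longitudinal analysis (11.4.2).** The relationship between QOL and the intervention "will be handled by repeated measures analysis of variance modeling and multiple regressions". On covariates: "The modeling processes will include the aforementioned covariates to control for spurious correlations". The only covariates named earlier in section 11 are the three in 11.3.2.
- **Time points.** The lead-in to the secondary endpoints in 11.4.1 lists "baseline and at 3 and 6 months after hospital discharge".
- **Power (11.2.1).** 194 patients, 97 per arm, with a 10% attrition allowance, are said to give 80% power for "a half standard deviation difference in QOL endpoints".

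No section names the baseline score as a covariate. None says whether baseline is a covariate, a response level or part of a change score, and no arm-by-visit term or target contrast is named.

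**The concern.** Length of stay is measured once, so its analysis has no use for a baseline value. QOL is measured before and after surgery, and a patient's baseline score usually predicts the later score on the same scale. Copying the length-of-stay analysis to QOL leaves that information out of the t-test and the linear models, although it has already been collected.

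The repeated-measures ANOVA may use baseline, but the text does not say how. Its power depends on how baseline enters. With that left open, analyses of different power remain available after the data are seen, for a trial in which QOL trajectory is a stated aim and the CRQ is the main QOL instrument.

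**Working it through.** **Inputs.** From 11.2.1 and 11.3.2: 97 per arm, 10% attrition, two-sided 0.05, target 0.5 SD. Evaluable per arm: 97 × 0.9 = 87.3, taken as 87. Assumed, because the documents give no figure: baseline-to-follow-up correlation ρ = 0.3, 0.5 or 0.7, the same SD at each visit and, for the two-visit results, equal correlation between all visits and the same effect at both follow-ups.

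**The plan's own figure.** For 0.5 SD at 80% power the normal formula gives 2 × (1.960 + 0.842)² / 0.5² = 62.8, so 63 per arm. Then 63/0.9 = 70 per arm, or 140 in total. With 87 per arm the noncentrality is 0.5 × √(87/2) = 3.30, and the noncentral t gives 90.6%. The claim of at least 80% therefore holds, with room to spare, for an unadjusted t-test.

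**One follow-up visit.** Noncentrality is 3.30/√V, where V is the variance relative to the raw follow-up score: V = 1 for raw scores, 1 − ρ² with baseline as covariate, 2(1 − ρ) for change scores. The reduction from adjustment is ρ² against raw scores and (1 − ρ)/2 against change scores.

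| ρ | V adjusted | Power adjusted | V change | Power change | Reduction v raw | Reduction v change |
|---|---|---|---|---|---|---|
| 0.3 | 0.91 | 93.0% | 1.40 | 79.1% | 9% | 35% |
| 0.5 | 0.75 | 96.6% | 1.00 | 90.6% | 25% | 25% |
| 0.7 | 0.51 | 99.6% | 0.60 | 98.9% | 49% | 15% |

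In standard errors, the reduction against raw scores is 5% to 29% (1 − √0.91 to 1 − √0.51).

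**Beyond the three named covariates.** The gain is then the squared partial correlation. As an illustration, suppose age, gender and lung function explain 10% of both scores through one shared index. The partial correlation is (ρ − 0.10)/0.90 = 0.222, 0.444 or 0.667, so the further reduction is 5%, 20% or 44%. Power is 93.3% with the three covariates and 94.4%, 97.1% or 99.6% with baseline added.

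**Both visits.**

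| Analysis | V | ρ = 0.3 | ρ = 0.5 | ρ = 0.7 |
|---|---|---|---|---|
| Mean of 3 and 6 months, no baseline | (1 + ρ)/2 | 98.2% | 96.6% | 94.5% |
| Same mean, baseline as covariate | (1 + ρ)/2 − ρ² | 99.2% | 99.6% | >99.9% |
| Same mean minus baseline (1 df) | 1.5(1 − ρ) | 89.3% | 96.6% | 99.8% |
| Arm-by-visit over three visits (2 df) | see below | 83% | 93% | >99% |

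For the 2-df test the noncentrality is 87 × 0.5² / [2 × 1.5(1 − ρ)] = 7.25/(1 − ρ), that is 10.4, 14.5 and 24.2. Part of its gap from the adjusted analysis comes from the extra degree of freedom, not from the handling of baseline.

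**CRQ in points.** 11.4.1 sets the CRQ target at 0.5 point and gives no SD. The difference detectable with 80% power is 0.427 SD, so the unadjusted test keeps 80% power for 0.5 point up to an SD of 0.5/0.427 = 1.17. With adjustment the limit is 1.23 to 1.64 over the assumed ρ.

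**The case against.** **The consequence is modest.** QOL is a secondary endpoint and the half-SD target is met without adjustment. This stands in full.

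**The documents hint at a role for baseline.** It is listed as a time point in 11.4.1, 11.4.2 plans a longitudinal model, and objective 2.2.2 speaks of a trajectory. A natural reading is baseline as a response level with interest in arm-by-visit, so baseline would not be ignored. This stands in part. The time-point list also covers postoperative complications, which have no baseline value, and it is not a model. If that reading is intended, much of the information is already used and the gain shrinks as the correlation rises: 83% against 99% at 0.3, but almost nothing at 0.7.

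**The size rests on assumed values.** The correlation, the 10% shared index and the equal correlation across surgery are all assumptions. True; the figures are conditional. Half an SD and 0.5 point are both tied to the sample size, which implies an SD of 1.0, so the 1.17 limit matters only if the real SD is larger.

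**A stronger reading.** A reader might infer that the plan will report the arm main effect over all three visits. Including the pre-treatment visit would shrink the effect to two thirds (0.333 SD) and, with V = (1 + 2ρ)/3, give power of 85%, 76% and 69% at ρ = 0.3, 0.5 and 0.7. No section plans that contrast, and objective 2.2.2 asks about 3 and 6 months, so this is not a finding against the plan.

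**Conclusion.** The omission is clear from the text: the baseline score is not among the named covariates, and its role in the repeated-measures ANOVA is not stated. The result is avoidable loss of precision on a secondary endpoint, plus an open choice between analyses of different power.

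A reader might infer that the unadjusted comparison is biased or that the QOL aim is underpowered. The documents support neither. Randomization protects the comparison of follow-up scores, and power for half an SD is about 91% with 87 per arm.

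The size is conditional on an assumed correlation of 0.3 to 0.7. At one visit the variance falls by 9 to 49% against raw scores and by 35 to 15% against change scores, with power of 93% to over 99%. Against a two-degree-of-freedom arm-by-visit test the comparison is 83%, 93% and over 99%, with 99% or more for the baseline-adjusted mean of both visits, under equal correlation and the same effect at both visits. Confidence is high on the omission and lower on the amount.

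**What to change.** In 11.4.1, replace the sentence that equates the QOL analysis with that of the primary endpoint, and state in 11.4.2 that the following is the repeated-measures analysis:

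> Each CRQ domain and each LASA item at 3 and 6 months is compared between arms in one repeated-measures model with arm, visit, arm-by-visit, the baseline score of the same scale, baseline-by-visit and the covariates of 11.3.2, using all available visits. The arm differences at 3 and at 6 months are reported. The CRQ remains the primary QOL tool.

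Also state:

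- **Missing baseline.** Impute the mean baseline score of both arms pooled. A constrained longitudinal model with equal baseline means in the two arms is a close alternative, not an identical one, and keeps these patients without imputation.
- **Skewed scores.** Keep the Wilcoxon provision of 11.3.2 as a sensitivity analysis, so that the new wording does not drop it unnoticed.
- **MRC.** Use an ordinal model adjusted for baseline grade.
- **Timing.** Use as baseline only scores completed before the arm is disclosed. Section 6.2 places the booklet at randomization but does not say on which side of disclosure.

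The cost is SAP wording, a little more analysis work and one rule for missing baseline scores. Baseline collection is already in the calendar, so no visit, form or patient is added; sites need only the instruction on timing.
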